2. ANALYSIS SETS

2.1 Definition of analysis sets

While some listings and tables may be produced based on all subjects screened, the following analysis population will be used for all analyses:

Safety Analysis Set (SAF): all enrolled patients who received at least 1 dose of durvalumab or tremelimumab.

2.2 Protocol Deviations

2.2.1 Important Protocol Deviations

According to ICH E3 guidelines version dated 1995 (ICH 1995),

"Protocol deviations consist of any change, divergence or departure from the study design or procedures defined in the protocol. Important protocol deviations (IPDs) are a subset of protocol deviations that may significantly affect the completeness, accuracy, and/or reliability of the study data or that may significantly affect a patient's rights, safety or well-being."

For the interim analysis, all major deviations were classified as important deviations. For the final analysis, 4 general categories will be considered IPDs and will be listed and summarised.

- Deviation 1: Patients who deviate from key entry criteria per the Clinical Study Protocol v5.0 (CSP).
 - Inclusion Criterion 7: No prior exposure to anti-PD-1 or anti-PD-L1, including on another AstraZeneca study. Exposure to other investigational agents may be permitted after discussion with the Sponsor.
 - Inclusion Criterion 8: Adequate organ and marrow function as defined below:
 - Hemoglobin ≥9.0 g/dL
 - Absolute neutrophil count $\geq 1.0 \times 109 / L$
 - Platelet count \geq 75 × 109/L

- Serum bilirubin ≤1.5 × the upper limit of normal (ULN). This will not apply to patients with confirmed Gilbert's syndrome, who will be allowed in consultation with their physician.
- ALT and AST ≤2.5 × ULN; for patients with hepatic metastases, ALT and AST≤5 × ULN
- Measured creatinine clearance (CL) >40 mL/min or Calculated creatinine clearance (CL) >40 mL/min as determined by Cockcroft-Gault (using actual body weight)
- Inclusion Criterion A1: Histologically or cytologically confirmed locally advanced or metastatic urothelial ornon-urothelial carcinoma of the urinary tract (including the urinary bladder, ureter, urethra and renal pelvis)
- Inclusion Criterion A2: Disease that has progressed during or after at least one previous platinum or non-platinum-based chemotherapy, either for PD less than 12 months after adjuvant or neoadjuvant chemotherapy, or metastatic disease
- Inclusion Criterion A3: ECOG performance status 0-2
- Exclusion Criterion 3: Concurrent enrollment in another clinical study, or another substudy of this protocol, unless it is an observational (non-interventional) clinical study or during the follow up period of an interventional study
- Exclusion Criterion 4: Participation in another clinical study with an investigational product during the last 28 days or 5 half-lives, whichever is longer, prior to the first dose of study treatment.
- Exclusion Criterion 5: Any concurrent chemotherapy, investigational agent, biologic, or hormonal therapy for cancer treatment. Concurrent use of hormonal therapy for non-cancer-related conditions (eg, hormone replacement therapy) is acceptable.
- Exclusion Criterion 7: Receipt of any investigational anticancer therapy within 28 days or 5 half-lives, whichever is longer, prior to the first dose of study treatment.
- Exclusion Criterion 8: Radiotherapy treatment to more than 30% of the bone marrow or with a wide field of radiation within 4 weeks of the first dose of study drug. Note: Local treatment of isolated lesions, excluding target lesions, for palliative intent is acceptable.
- Exclusion Criterion 9: Major surgical procedure (as defined by the Investigator) within 28 days prior to the first dose of IP. Note: Local surgery of isolated lesions for palliative intent is acceptable.
- Exclusion Criterion 10: History of allogenic organ transplantation.
- Exclusion Criterion 11: Uncontrolled intercurrent illness, including but not limited to, ongoing or active infection, symptomatic congestive heart failure, uncontrolled hypertension, unstable angina pectoris, cardiac arrhythmia, ILD, serious chronic GI conditions associated with diarrhea, or psychiatric illness/social situations that would limit compliance with study requirement, substantially increase risk of incurring AEs or compromise the ability of the patient to give written informed consent.
- Exclusion Criterion 12: History of another primary malignancy except for

- Malignancy treated with curative intent and with no known active disease ?5 years before the first dose of investigational product (durvalumab + tremelimumab) and of low potential risk for recurrence
- Adequately treated non-melanoma skin cancer or lentigo maligna without evidence of disease
- Adequately treated carcinoma in situ without evidence of disease
- Exclusion Criterion 13: History of leptomeningeal carcinomatosis
- Exclusion Criterion 14: Has untreated central nervous system (CNS) metastases and/or carcinomatous meningitis identified either on baseline brain imaging (please refer to RECIST for details on the imaging modality) obtained during the screening period or identified prior to signing the ICF. Patients whose brain metastases have been treated may participate provided they show radiographic stability (defined as 2 brain images, both of which are obtained after treatment to the brain metastases. These imaging scans should both be obtained at least 4 weeks apart and show no evidence of intracranial progression). In addition, any neurologic symptoms that developed either as a result of the brain metastases or their treatment must have resolved or be stable either, without the use of steroids, or are stable on a steroid dose of ?10 mg/day of prednisone or its equivalent and anti-convulsants for at least 14 days prior to the start of treatment. Brain metastases will not be recorded as RECIST Target Lesions at baseline.
- Exclusion Criterion 15: History of active primary immunodeficiency.
- Exclusion Criterion 16: Active infection including tuberculosis (clinical evaluation that includes clinical history, physical examination and radiographic findings, and tuberculosis testing in line with local practice), hepatitis B (known positive hepatitis B virus [HBV] surface antigen (HBsAg) result), hepatitis C, or human immunodeficiency virus (positive HIV 1/2 antibodies). Patients with a past or resolved HBV infection (defined as the presence of hepatitis B core antibody [anti-HBc] and absence of HBsAg) are eligible. Patients positive for hepatitis C virus (HCV) antibody are eligible only if polymerase chain reaction is negative for HCV RNA.
- Exclusion Criterion 17: Current or prior use of immunosuppressive medication within 14 days before the first dose of durvalumab or tremelimumab. The following are exceptions to this criterion:
 - Intranasal, inhaled, topical steroids, or local steroid injections (eg, intra articular injection)
 - Systemic corticosteroids at physiologic doses not to exceed 10 mg/day of prednisone or its equivalent
- Exclusion Criterion 18: Active or prior documented autoimmune or inflammatory disorders (including inflammatory bowel disease [eg, colitis or Crohn's disease], diverticulitis [with the exception of diverticulosis], systemic lupus erythematosus, Sarcoidosis syndrome, or Wegener syndrome [granulomatosis with polyangiitis, Graves' disease, rheumatoid arthritis, hypophysitis, uveitis, etc.]). The following are exceptions to this criterion:
 - Patients with vitiligo or alopecia

- Patients with hypothyroidism (eg, following Hashimoto syndrome) stable on hormone replacement
- Any chronic skin condition that does not require systemic therapy
- Patients without active disease in the last 5 years may be included but only after consultation with the study physician
- Patients with celiac disease controlled by diet alone.
- Exclusion Criterion 20: Known allergy or hypersensitivity to study drug(s) or compounds of similar biologic composition to the study drug(s), or any of the study drug excipients.
- Exclusion Criterion 21: Any unresolved NCI CTCAE Grade ≥2 toxicities from prior anti-cancer therapy with the exception of vitiligo, alopecia, and the laboratory values defined in the inclusion criteria.
 - Patients with Grade ≥2 neuropathy will be evaluated on a case-by-case basis after consultation with the Study Physician.
 - Patients with irreversible toxicity not reasonably expected to be exacerbated by treatment with durvalumab or tremelimumab may be included only after consultation with the Study Physician
- Exclusion Criterion 24: Prior randomization or treatment in a previous durvalumab and/or tremelimumab clinical study regardless of treatment arm assignment.
- Exclusion Criterion A1: Any other malignancy within 5 years before first dose of IP, except for the following:
 - Patients with a history of prostate cancer (tumor/node/metastasis stage) of stage ≤T2cN0M0 without biochemical recurrence or progression and who in the opinion of the Investigator are not deemed to require active intervention
 - Patients who have been adequately treated for a malignancy with a low potential risk for recurrence, eg, cervical carcinoma in situ, non-melanomatous carcinoma of the skin, or ductal carcinoma in situ of the breast that has been surgically cured
- Deviation 2: Patients who met discontinuation criteria (per CSP Section 3.9) but did not discontinue durvulumab.
- Deviation 3: Received prohibited concomitant medications (including other anti-cancer agents). Please refer to the CSP section 7.7 for those medications that are detailed as being 'excluded' from permitted use during the study. This will be used as a guiding principle for the physician review of all medications prior to database lock to identify those likely have an impact on efficacy.
- Deviation 4: A pattern of two or more missed treatments, safety and/or efficacy assessments observed in an individual patient or group of patients that, in the opinion of the principal investigator,
 - were due to the 2020 COVID-19 global pandemic and,
 - had a significant effect on either the completeness, accuracy, and/or reliability of the patient's data, or the patient's rights, safety or well-being.

2.2.2 Monitoring of Important Protocol Deviations

The categorisation of IPDs is not automatic and will depend on duration and the perceived effect on study endpoints.

In addition to the programmatic determination of IPDs, monitoring notes or summaries will be reviewed to determine any important post entry deviations that are not identifiable via programming, and to check that those identified via programming are correctly classified. The final classification of deviations will be made prior to database lock or data freeze. Decisions made will be documented and approved by AstraZeneca prior to analysis.

3. PRIMARY AND SECONDARY VARIABLES

3.1 Safety

The primary outcome measure for the study is the number and proportion of patients with AESI. Pre-defined Medical Dictionary for Regulatory Activities (MedDRA) preferred terms groupings will be used to identify AESI.

'On treatment' will be defined as assessments between date of first dose and 90 days following last dose inclusive.

3.1.1 Adverse Events (AEs)

AEs and SAEs will be collected throughout the study, from time of signature of informed consent and up to 90 days after the last dose of immunotherapy agents (ie, the last dose of durvalumab or tremelimumab). MedDRA (using the latest or current MedDRA version) will be used to code the AEs. AEs will be graded according to the National Cancer Institute (NCI) Common Terminology Criteria for AEs (CTCAE Version 4.03).

A treatment emergent adverse event (TEAE) is an AE with an onset date or a pre-existing AE worsening following the first dose of study treatment through to 90 days after the last dose of immunotherapy agents. For the durvalumab + tremelimumab modules, in the event of the components being administered separately, then date of first dose/last dose will be considered as the earliest/latest dosing date of either component. Any AE occurring before study treatment (i.e. before the administration of the first dose on Study Day 1) will be included in the AE listings, but will not be included in the summary tables (unless otherwise stated). These will be referred to as 'pre-treatment'. However, any AE occurring before the administration of the first dose on Study Day 1 that increases in severity after the first dose will be regarded as treatment emergent and thus will be included in the majority of summary tables.

For patient level summaries, if more than one AE is coded to the same PT for the same patient, the patient will be counted only once in summaries using the most serious grading on causal relationship to study treatment.

3.1.1.1 Primary endpoint - AESI

An AESI is one of scientific and medical interest specific to understanding of the Investigational Product and may require close monitoring and rapid communication by the

investigator to the sponsor. An AESI may be serious or non-serious. The rapid reporting of AESIs allows ongoing surveillance of these events in order to characterize and understand them in association with the use of this investigational product.

AESIs observed with durvalumab or tremelimumab include pneumonitis, hepatitis, diarrhea/colitis, intestinal perforation, endocrinopathies (hypo- and hyperthyroidism, adrenal insufficiency, hypophysitis/hypopituitarism and type I diabetes mellitus), nephritis, rash/dermatitis, myocarditis, myositis/polymyositis, pancreatitis, and rare/less frequent imAEs including neuromuscular toxicities such myasthenia gravis and Guillain-Barré syndrome. Other inflammatory responses that are rare/less frequent with a potential immune-mediated etiology include, but are not limited to pericarditis, sarcoidosis, uveitis and other events involving the eye, skin, hematological and rheumatological events, vasculitis, non-infectious meningitis and non-infectious encephalitis. It is possible that events with an inflammatory or immune mediated mechanism could occur in nearly all organs. In addition, infusion-related reactions and hypersensitivity/anaphylactic reactions with a different underlying pharmacological etiology are also considered AESIs.

Other categories may be added or existing terms may be merged as necessary. An AstraZeneca medically qualified expert after consultation with the Global Patient Safety Physician has reviewed the AEs of interest and identified which preferred terms contribute to each AESI. A further review will take place prior to Database lock (DBL) by a medically qualified expert in collaboration with AstraZeneca to ensure any further terms not already included are captured within the categories.

Immune-mediated AEs

AESIs for durvalumab or tremelimumab include but are not limited to events with a potential inflammatory or immune-mediated mechanism and which may require more frequent monitoring and/or interventions such as steroids, immunosuppressants and/or hormone replacement therapy. An imAE is defined as a subset of AESIs which are associated with drug exposure and is consistent with an immune-mediated mechanism of action and where there is no clear alternate aetiology.

The identification of imAEs will be made following the AstraZeneca imAE characterization charter (see Appendix 1).

For the DMC safety review, imAEs will be identified through:

- the selection of preferred term

For the interim and final analysis of each module, imAEs will be identified through:

- the selection of preferred term,
- programmatic identification of those potential imAEs requiring medication such as steroids, immunosuppressants and/or hormone replacement therapy

3.1.1.2 Other Significant Adverse Events

During the evaluation of the AE data, a medically qualified expert will review the list of AEs that were not reported as SAEs and 'Discontinuation of Investigational Product due to Adverse Events' (DAEs). Based on the expert's judgment, significant AEs of particular

clinical importance may, after consultation with the Global Patient Safety Physician, be considered other significant adverse events (OAEs) and reported as such in the Clinical Study Report (CSR). A similar review of laboratory/vital signs/ECG data will be performed for identification of OAEs.

Examples of these are marked hematological and other laboratory abnormalities, and certain events that lead to intervention (other than those already classified as serious) or significant additional treatment.

3.1.1.3 Designated Medical Events

A pre-defined non product specific list of MedDRA terms used within the business will be provided prior to any database lock, which will be used to summarise specific adverse events for use in PSUR (Periodic Safety Update Report), ePSUR, DSUR (Development Safety Update Report) or SMS (Signal Management System).

3.1.2 Secondary Safety Endpoints

3.1.2.1 Treatment exposure

Exposure will be defined as follows:

Total (or intended) exposure of study treatment

• Total (or intended) exposure = [earliest of (last dose date where dose > 0 mg +28 days, death date, DCO date] – first dose date + 1

Actual exposure of study treatment

• Actual exposure = intended exposure – total duration of dose interruptions, where intended exposure will be calculated as above.

Dose reductions are not permitted per section 6.9.1 of the core CSP. The actual exposure calculation makes no adjustment for any dose reductions that may have occurred.

Exposure will also be measured by the number of cycles received. For each immunotherapy agent a cycle corresponds to one dose of treatment. A cycle will be counted if treatment is started even if the full dose is not delivered.

3.1.2.2 Patients who permanently discontinue during a dose interruption

If a decision is made to permanently discontinue study treatment in-between cycles or during a cycle delay then the date of last administration of study medication recorded will be used in the programming.

3.1.2.3 Laboratory data

Laboratory data will be collected throughout the study, from screening to the follow-up visits as described in the CSP. Blood and urine samples for determination of haematology, clinical chemistry, and urinalysis will be collected as described in section 5.3.1 of the CSP. For the definition of baseline and the derivation of post baseline visit values considering visit window and how to handle multiple records, derivation rules as described in section 3.1.3 below will be used.

Change from baseline in haematology and clinical chemistry variables will be calculated for each post-dose visit on treatment. CTC grades will be defined at each visit according to the CTC grade criteria using local or project ranges as required, after conversion of lab result to corresponding preferred units. The following parameters have CTC grades defined for both high and low values: Potassium, Sodium, and Glucose so high and low CTC grades will be calculated.

Absolute values will be compared to the project reference range and classified as low (below range), normal (within range or on limits of range) and high (above range). The maximum or minimum on-treatment value (depending on the direction of an adverse effect) will be defined for each laboratory parameter as the maximum (or minimum) post-dose value at any time.

Local reference ranges will be used for the primary interpretation of laboratory data at the local laboratory. Project (AZ standard) reference ranges will be used throughout for reporting purposes. The denominator used in laboratory summaries of CTC grades will only include evaluable patients, in other words those who had sufficient data to have the possibility of an abnormality.

For example:

- If a CTCAE criterion involves a change from baseline, evaluable patients would have both a pre-dose and at least 1 post-dose value recorded.
- If a CTCAE criterion does not consider changes from baseline, to be evaluable the patient need only have 1 post dose-value recorded.

3.1.3 General considerations for safety assessments

Time windows will be defined for any presentations that summarise values by visit using the following conventions:

- The time windows should be exhaustive so that data recorded at any time point has the potential to be summarised. Inclusion within the time window should be based on the actual date and not the intended date of the visit.
- All unscheduled visit data should have the potential to be included in the summaries. The window for the visits following baseline will be constructed in such a way that the upper limit of the interval falls half way between the two visits (the lower limit of the first post-baseline visit will be Day 2). If an even number of days exists between two consecutive visits then the upper limit will be taken as the midpoint value minus 1 day.

For example, the visit windows for vital signs data (with 4 weeks between scheduled assessments) are:

Day 29, visit window 2 - 42

Day 57, visit window 43 - 70

Day 85, visit window 71 - 98

Day 113, visit window 99 – 126

Day 141, visit window 127 – 154

Day 169, visit window 155 – 182

Day 197, visit window 183 – 210

Day 225, visit window 211 – 238

> Day 253, visit window 239 – 266 Day 281, visit window 267 – 294 Day 309, visit window 295 – 322 Day 337, visit window 323 – 350

- For summaries showing the maximum or minimum values, the maximum/minimum value recorded on treatment will be used (regardless of where it falls in an interval).
- Listings should display all values contributing to a time point for a patient.
- For visit based summaries:
 - If there is more than one value per patient within a time window then the closest value to the scheduled visit date should be summarised, or the earlier in the event the values are equidistant from the nominal visit date, or the average if it is not possible to ascertain the earliest. The listings should highlight the value for that patient that went into the summary table, wherever feasible. Note: in summaries of extreme values all post baseline values collected are used including those collected at unscheduled visits regardless of whether or not the value is closest to the scheduled visit date.
 - To prevent very large tables or plots being produced that contain many cells with sparse data that is difficult to interpret, for each treatment group visit data should only be summarised if the number of observations is greater than the minimum of 20 and > 1/3 of patients dosed.
- For summaries at a patient level, all values should be included, regardless of whether they appear in a corresponding visit based summary, when deriving a patient level statistic such as a maximum.
- Baseline will be defined as the last non-missing measurement prior to dosing with study treatment (excluding unscheduled visit). For the re-treatment period for immunotherapy agents then baseline is similarly defined as the last non-missing measurement prior to the first dose on the re-treatment period. For laboratory data, any assessments made on day 1 will be considered pre-dose. Alternatively, if two visits are equally eligible to assess patient status at baseline (e.g., screening and baseline assessments both on the same date prior to first dose with no washout or other intervention in the screening period), the average can be taken as a baseline value. For non-numeric laboratory tests (ie some of the urinalysis parameters) where taking an average is not possible then the best value would be taken as baseline as this is the most conservative. In the scenario where there are two assessments on day 1, one with time recorded and the other without time recorded, the one with time recorded would be selected as baseline. Where safety data are summarised over time, study day will be calculated in relation to date of first treatment.
- Missing safety data will generally not be imputed. However, safety assessment values of the form of "< x" (i.e., below the lower limit of quantification) or > x (i.e., above the upper limit of quantification) will be imputed as "x" in the calculation of summary statistics but displayed as "< x" or "> x" in the listings.
- For missing diagnostic dates, if day and/or month are missing use 01 and/or Jan. If year is missing, put the complete date to missing.
- For missing concomitant medication and AE start dates:
 - If year is missing (or completely missing), do not impute.

- If year is present and months and day are missing; or year and day are present and month is missing, impute as January 1st.
- If year and month are present and day is missing, impute day as first day of the month.
- For missing concomitant medications and AE end dates, the following will be applied:
 - If year is missing (or completely missing), do not impute.
 - If year is present and month and day are missing; or year and day are present and month is missing, impute as December 31st.
 - If year and month are present and day is missing, impute day as last day of the month.
 - When the patient has died in the same month/year of partial stop date, use date of death.
- For medications, a conservative approach will be followed and events will be assumed to be concomitant unless the end date is before the first dose of IP. If the start and end dates are both missing it is considered concomitant.
- In addition for AEs if, for a partial start date, the AE start date could (when also considering the AE end date) potentially be on the first study treatment date, the AE start date will be imputed with the first study treatment date to assume a "worst case" scenario; e.g. AE from UNK-Jun-2017 to 23-Jul-2017 with the first study treatment date 21-Jun-2017, then the AE start date will be imputed to 21-Jun-2017.

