3.4 Baseline

3.4.1 Prior and concomitant medications

The WHO Drug B3 dictionary will be used for concomitant medication coding.

Any medications taken by the patient prior to the first dose date of study treatment will be considered prior medication.

Any medication taken by the patient at any time after the date of the first dose (including the date of the first dose) of study treatment up to 90 days after last dose will be considered concomitant medication. Any medication that started prior to the first dose of study treatment and ended after the first dose or is ongoing will be considered as both prior and concomitant medication.

For the purpose of inclusion in prior or concomitant mediation summaries, incomplete medication start and stop dates will be imputed as detailed in Section 3.1.3.

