- PDL1: high >=25% vs low <25%. If data is available from the central laboratory, the central laboratory result will be used in the group derivation, otherwise, the local test result will be used.

Subgroup analyses will also be conducted for the summary of OS, ORR and DCR in the following subgroups of the SS:

- Age at baseline: <65 vs 65-74 vs ≥ 75 years of age
- ECOG performance status at baseline: 0-1 vs 2
- Primary tumor location: Bladder vs Renal pelvis and Ureter vs Urethra vs Other
- Stage: III vs IV
- Tumor histology: Urothelial (i.e. TCC) vs non-urothelial
- Previous platinum chemotherapy: platinum vs non-platinum chemotherapy
- Best response to previous therapy (CR vs PR vs SD vs PD)

- Baseline metastases: liver (+/- other visceral or non-visceral metastases) vs lymph node metastases only
- PDL1: high \geq 25% vs low \leq 25%

No formal comparisons will be performed between the subgroups.

Time-to-event analyses

Time-to-event of AESI and imAE:

Time-to-onset of AESI/imAE (by AESI/imAE category) and time-to-intervention with steroids, immunosuppressants and/or hormone replacement therapy to treat an AESI/imAE will be defined as time from first dose of durvalumab +/- tremelimumab to first onset of the event.

Time-to-event (TTE) is defined in months as follows:

TTE (months) = (Date of event or censoring–Date first dose of durvalumab [durvalumab + tremelimumab for the combinations modules]+1)/(365.25/12)

Time-to-resolution (TTR) of an AESI/imAE type is defined as the time from the first onset of an AESI/imAE type to the resolution of the AESI/imAE type. TTR is defined in months as follows:

TTR (months) = (Date of AESI/imAE resolution or censoring–Date of AESI/imAE onset+1)/(365.25/12)

Analysis of TTR will only include patients who have experienced an AESI/imAE.

The distribution of TTE and TTR times will be estimated using the Kaplan-Meier method (Kaplan and Meier 1958) and summarised using the median, twenty-fifth and seventy-fifth percentiles. TTE and TTR of imAE of NCI CTCAE grade >=3 will also be produced.

Deaths

A summary of deaths will present number (n) and percentage (%) of patients for the following categories:

- Total number of deaths (including deaths occurring within 90 days after last dose of study medication and deaths occurring after the 90 days post dosing window)

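### SAP 3.1.3 sets no floor at AE onset for a treating drug's partial start date, so the drug can be dated before the AE it was given for

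*SAP*

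**What the plan says.** SAP 3.1.3 gives one start-date rule for concomitant medications and AEs. With the day missing: "If year and month are present and day is missing, impute day as first day of the month". With the month missing: "year and day are present and month is missing, impute as January 1st". End dates go the other way: "If year and month are present and day is missing, impute day as last day of the month", or 31 December when the month is missing, with date of death used when the patient died in that month.

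A further rule applies to AEs only. If a partial onset could fall on the day of first dose, "the AE start date will be imputed with the first study treatment date". The SAP's example is an AE from UNK-Jun-2017 to 23-Jul-2017 with "the first study treatment date 21-Jun-2017, then the AE start date will be imputed to 21-Jun-2017". No such rule is given for medications, and nothing ties a medication's start to the AE it was given for.

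The medication dates are used, or may be used, in these places:

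- SAP 3.4.1: "Any medications taken by the patient prior to the first dose date of study treatment will be considered prior medication". The same section counts a drug that began before first dose and ended after it, or is ongoing, as both prior and concomitant. It applies the 3.1.3 imputation to these summaries. SAP 4.2.3 selects the prior-medication table on a start date before treatment start.
- SAP 4.2.1, AESI section: length of intervention with steroids, immunosuppressants or hormone replacement is calculated from the treatment's start and stop dates.
- SAP 4.2.1, time-to-event analyses: "time-to-intervention with steroids, immunosuppressants and/or hormone replacement therapy to treat an AESI/imAE will be defined as time from first dose". That sentence covers time-to-onset as well, and it ends both intervals at the event's first onset.

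**The concern.** A drug started because of an AE cannot begin before that AE. The date rules allow this order in two ways. Near first dose, the AE is moved forward to first dose while the drug stays at the start of the month or year. Later in treatment, a fully dated AE may fall mid-month while the drug's missing day is set to the 1st.

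The outputs at stake describe how AESIs were treated, which belongs to the primary objective (Protocol 2.1 and SAP 1.1.1 both name intervention/treatment). A drug used for a treatment-emergent event can appear in the prior-medication table, and length of intervention can include days before the event existed. Because starts are imputed early and ends late, any error in length runs one way, towards longer courses.

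The end point of time-to-intervention is a separate matter. Read literally, it is the same quantity as time-to-onset and says nothing about when treatment began.

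**Working it through.** **Inputs.** Start, end and AE-only rules from SAP 3.1.3; prior/concomitant rules from 3.4.1 and the default in 3.1.3 (concomitant unless the end date precedes first dose); the time-to-event formula from 4.2.1, (date − first dose + 1)/(365.25/12), where 365.25/12 = 30.4375 days per month. The SAP gives no formula for length of intervention, so I assume end − start + 1. The 20-day difference below does not depend on the +1.

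**1. The SAP's example.** AE UNK-Jun-2017 to 23-Jul-2017, first dose 21-Jun-2017. June 2017 contains the first dose date and the AE ended after it, so the AE start becomes 21-Jun-2017. This reproduces the stated result.

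**2. A drug given for that AE, ending 23-Jul-2017.**

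| Recorded drug start | Date used | Days from AE onset | Class | Length (days) |
|---|---|---|---|---|
| UNK-Jun-2017, as written | 1-Jun-2017 | 1 − 21 = −20 | prior and concomitant | 30 + 23 = 53 |
| year 2017 only, as written | 1-Jan-2017 | −171 | prior and concomitant | 204 |
| either, floored at AE onset | 21-Jun-2017 | 0 | concomitant only | 10 + 23 = 33 |

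Excess length: 53 − 33 = 20 days, or 204 − 33 = 171 days.

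**3. A fully dated AE later in treatment.** AE on 20-Aug-2017, drug UNK-Aug-2017, same first dose. The drug is set to 1-Aug-2017, 19 days before its AE. Since 1-Aug is after first dose, it is concomitant only. Prior status therefore needs an imputed date before first dose: a missing day in the first-dose month (unless first dose is on the 1st), or a missing month in the first-dose year (unless first dose is on 1 January).

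**4. Largest gap.** If drug and AE fall in the same month, a missing day can place the drug at most 31 − 1 = 30 days before the AE. If they fall in the same year, a missing month can place it at most 365 − 1 = 364 days before (365 in a leap year).

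**5. Can the drug become prior only?** That requires an imputed end before first dose. An imputed end, including one set to date of death, is never earlier than the true end, so a drug truly started on or after first dose cannot lose concomitant status. A grid of 34,200 cases agreed: true starts 0 to 189 days after first dose, true ends 0 to 57 days after start in steps of 3, and start and end each complete, day-missing or month-missing. It gave 0 prior-only cases; death capping was not part of the grid.

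**6. Time-to-intervention.** If the interval ended at drug start, step 2 would give (−20 + 1)/30.4375 = −0.62 months for the missing day and (−171 + 1)/30.4375 = −5.59 months for the year-only date. With the floor it is (0 + 1)/30.4375 = 0.03 months. Under the SAP's literal end point the drug date does not enter.

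**The case against.** Much can be said for leaving this alone. The study is descriptive, with no hypothesis tests, and AESI incidence, the primary outcome measure, uses no medication dates. Protocol 9.4 has queries raised for missing data, so partial dates may be few. SAP 3.4.1 ties medication-date imputation expressly to the prior and concomitant summaries, while 4.2.1 does not say that imputed dates enter length of intervention. These points stand and keep the matter small. On the last one, if 3.1.3 does not govern length of intervention, the SAP has no stated rule there for partial dates, and one is still needed.

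Three stronger readings are tempting and are not supported:

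- *The drug is reclassified from concomitant to prior.* It is counted as both (3.4.1 and the default in 3.1.3), and prior status arises only as in step 3.
- *The SAP produces negative times to intervention.* It does so only if the interval ends at drug start, which is not what 4.2.1 literally says.
- *Identification of imAEs is compromised.* SAP 3.1.1.1 uses preferred terms and the need for medication, following a charter that is not in the text available here. The CRF records whether treatment was given for each AE (Protocol 6.3.3) and the dose, route and duration of drugs used to manage AESIs (Protocol 7.7). The link may therefore not use dates at all.

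A plain later-of rule would also do harm. It could move a drug recorded in February to an AE on 20 March, or move a genuine baseline hormone replacement to AE onset. The fix has to prevent both.

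**Conclusion.** The point holds in a limited form. The stated date rules can place a drug before the AE it treats. In the SAP's own example the gap is 20 days with the day missing and 171 days with only the year known. The drug is then tabulated as prior in addition to concomitant. If 3.1.3 dates feed length of intervention, the course is 53 or 204 days instead of 33. Partial dates in months after first dose can still precede the AE and lengthen the course, without prior status.

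These figures assume a drug recorded as ending 23-Jul-2017 and an inclusive day count. The number of partial medication dates is not given, so no study-level size can be stated. The duplicated end point in 4.2.1 is a separate drafting fault that exists even if every date is complete. Both are minor, and worth correcting because the remedy is cheap.

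**What to change.** - **SAP 3.1.3.** Add: for a medication recorded as started to treat an AE, if the current rule's date is earlier than that AE's (imputed) start date, use the AE start date, but only where the recorded month and year and the medication end date allow it; otherwise keep the current rule. A drug recorded in a month before the AE, or a baseline drug not started for the AE, is then left unchanged.
- **SAP 4.2.1, length of intervention.** State that the same dates are used.
- **SAP 4.2.1, time-to-intervention.** Define it as first dose to the start date of the first steroid, immunosuppressant or hormone replacement given for the AESI/imAE.

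Cost: a few sentences in the SAP and minor programming. No new data are needed.
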